- **3. Intent to treat analysis:** primary and secondary outcome data will be collected in all patients regardless of treatment received.⁸⁴ An "intent-to-treat" approach will be used for all primary/secondary outcome analyses, i.e., we will compare the outcomes of the two groups according to the group assignment at time of randomization, regardless of what treatment participants actually received. Phase 2 trial, this approach will allow a preliminary evaluation of the

effectiveness of the proposed treatment (in addition to the efficacy assessment), since the health care of the subjects reflects the health care available to civilian trauma. More details are given in the sections describing statistical analysis as well as the missing data prevention and treatment.⁸⁴

In addition to the "intent to treat" approach, this study design also supports that exploratory analyses assess the association between the dose of plasma received in the field and the primary/secondary outcomes, an equivalent to the estimand "Outcome Improvement in Tolerators" described by the Panel on Handling Missing Data in Clinical Trials.⁸⁴ This will provide information on possible "dose-response" patterns for Phase 3 trials.

- 4. Power analysis: Power analyses for each primary endpoint in Stage I and II were performed using Pass 11 (Hintze, J. (2011). PASS 11. NCSS, LLC. Kaysville, Utah, USA. www.ncss.com). All power analyses account for two interim analyses for a total of three sequential, equally spaced analyses, assuming attrition rates of 0%, 10%, and 20%.
- 5. Interim analyses: We planned 5 analyses (4 interim, 1 final), equally spaced, using the O'Brien-Fleming method to calculate two-sided boundaries, assuming a 95% confidence and 80% power. Spacing will be defined by number of enrolled patients. The first look at the data will be done when one third of the predicted total enrollment has been reached and all patients accrued have been observed for the total 28-day period or till death, whatever occurs earlier. The first interim analysis will be conducted when n=50, the second at n=100, the third at n=150, the fourth at n=200 and the final at end of the 5-year period of accrual.

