Boundaries will be used to declare a statistically significant difference between the two groups at an earlier stage without inflating the overall experiment errors. These interim analyses will be conducted by [name] and [name] using SAS vs. 9.3 data and reported to the DSMB, both in table format and in user-friendly graphs illustrating the test score, rejection and acceptance regions, as in the example below:

At each interim stage, if the test statistic falls into a rejection zone, the null hypothesis may be rejected and the DSMB will use this as one of the criteria for recommending early interruption of the trial. Otherwise, the trial continues to the next stage. At the final stage, the null hypothesis is rejected if Z falls into a rejection region. Otherwise, the null hypothesis is not rejected. In the example illustrated in the figure, the test statistic does not fall into the rejection regions for looks 1 and 2, and so the trial continued to the final analysis 3 when the test statistic fell into the rejection region, and the null hypothesis was rejected.

The results of the interim analyses described above will be just one of the criteria used by the DSMB to recommend early interruption of the trial as explained in more detailed later in this document.

- 6. Covariates for analysis: Please see description of randomization effectiveness for more details. (Section IV.D.2) In brief, potential covariates include: demographic variables (age, gender), injury severity (Injury Severity Score, blunt versus penetrating mechanism), degree of shock (Field SBP, Field Heart rate, Field Hematocrit), and a field coagulation measure (Field INR). We will adjust the analyses of endpoints only for the above-mentioned covariates showing different distribution (either statistically significant difference at p<0.05 or clinically significant difference as determined by the DSMB).

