- c. **Statistical Analysis**: The Fisher Exact test will be use to compare 28day mortality in the two groups. Statistical significance will be determined according to the interim analyses procedures describe below. If adjustment for pre-defined confounders is needed, we will use the above-defined method for categorical, binary variables.
- d. **Interim analyses:** We planned 5 analyses (4 interim, 1 final), equally spaced, using the O'Brien-Fleming method to calculate two-sided boundaries, assuming a 95% confidence and 80% power. All patients entered in each interim analyses will have complete data on 28-day mortality (i.e., the analyses will be conducted only once the 28-day observation period for all survivors have been completed).
- e. **Sample Size and Power:** This is a Phase 2 trial and is powered to detect large (17 to 19 percent-point) differences in mortality between the two groups.

Primary endpoint power calculations: 28-day mortality

Assumptions: 80% power, 95% confidence, 2-tailed test, P2=mortality in control group, P1=mortality in experimental group; 3 equally spaced data analyses, as determined by number of patients enrolled (2 interim when 1/3 and 2/3 of the predicted sample or 20 and 40 patients were enrolled, and a final when 60 to 75 patients were enrolled), using the O'Brien-Fleming method; control group 30-day mortality of 26% (based on control arm of ROC HS trial⁶⁷) and three attrition rates (0, 10%, 20%)

	Power	N1	N2	Alpha	Beta	P1	P2	Difference	Attrition Rate
	0.800000	60	60	0.050000	0.200000	0.07	0.26	0.19	20%
	0.800000	68	68	0.050000	0.200000	0.08	0.26	0.18	10%
L	0.800000	75	75	0.050000	0.200000	0.09	0.26	0.17	0%

Sample size of 60 and 60 achieves 80% power to detect a difference of 0.19 between the group proportions at a significance level (alpha) of 0.05 using a two-sided test. These results assume that 3 sequential tests are made using the O'Brien-Fleming spending function to determine the test boundaries, as seen below.

Boundaries (Bndry) for data looks Details when Spending = O'Brien-Fleming, N1 = 60, N2 =60, P1 = 0.07, P2 = 0.26 Lower Upper Nominal Inc Total Inc Total

^{*} Although the hypothesis is worded as "higher", all tests will be two-tailed to control for differences in either direction (higher or lower than the other group).

Look	Bndry	Bndry	Alpha	Alpha	Alpha	Power	Power
1	-3.71030	3.71030	0.000207	0.000207	0.000207	0.018650	0.018650
2	-2.51142	2.51142	0.012025	0.011890	0.012097	0.398801	0.417451

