There are several explanations for the differences in the expected and observed values. First, for the most common injury mechanisms, the case-fatality rate is decreasing in our trauma center ([name] et al. JAMA, 2016). Second, the wide use of TEG-guided hemostatic resuscitation in our institution has been associated with a dramatic decrease in post-injury mortality (Gonzalez, Ann Surg, 2016). In addition, our findings are not isolated. A recent multicenter RCT (Connelly et al., JAMA Surgery, 2016) also noted that the patients enrolled were less severely injured than anticipated based on previous experiences. Given the time required to establish such intense trials, usually one to two years, the assumptions used in the calculation of the sample size can understandably become outdated. This has prompted proposals of alternative designs for RCTs, such as adaptive and Bayesian RCTs as recently described by an NIH-funded workshop (Coffey et al. Clinical trials, 2012).

Based on the explanations above, we propose a continuation of the trial to increase sample size and make it adequate to detect differences in the proposed outcomes (mortality, admission acidosis and coagulation, hemorrhage as well as requirement for blood products), as follows:

Hypothesis for primary endpoint above: 28-day mortality will be significantly higher in control patients compared to experimental patients.

With 80% power, 95% confidence and assuming 12% mortality rate in the control group (based on the second interim analyses data), with 5 interim analyses (4 interim and 1 final, of which 3 already occurred), we will require 112 patients in each group (assuming the attrition rate observed in this RCT of 12%) to detect a difference of 10 percent points. This results in a total of 224 patients, which corresponds to an increase of 74 patients over the current sample size of 150 patients. See below the significance level for the 5 analyses.

Spending = O'Brien-Fleming, N1 = 112, N2 =112, P1 = 0.12, P2 = 0.02, Continuity Correction.

		Lower	Upper	Nominal	Inc	Total	Inc	Total
Look	Time	Bndry	Bndry	Alpha	Alpha	Alpha	Power	Power
1	0.20	-4.87688	4.87688	0.000	0.000	0.000	0.00015	0.000
2	0.40	-3.35695	3.35695	0.001	0.001	0.001	0.05885	0.059
3	0.60	-2.68026	2.68026	0.007	0.007	0.008	0.25750	0.317
4	0.80	-2.28979	2.28979	0.022	0.017	0.024	0.28890	0.605
5	1.00	-2.03100	2.03100	0.042	0.026	0.050	0.19460	0.800

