Hypothesis 5: Admission clot strength (as measured by TEG G) will be significantly lower in control patients compared to experimental group patients

With 80% power, 95% confidence and assuming mean admission TEG G = 7 dynes/cm² with standard deviation of 3 in the control group (based on the second interim analyses data), with 5 interim analyses (4 interim and 1 final, of which 3 already occurred), we will require 112 patients in each group (assuming the attrition rate observed in this RCT of 12%) to detect a difference of 1.1 dynes/cm² (from 7 to 5.9 dynes/cm²) between the two mean TEG Gs. This results in a total of 224, which corresponds to an increase of 74 patients over the current sample size of 150 patients.

F. Secondary Study Objectives and Endpoints

1. Secondary Objective 1: To determine the efficacy of postinjury field – resuscitation with plasma first compared to the current standard of care on

decreasing the incidence of adverse outcomes (as measured by a composite outcome including multiple organ failure and/or 28-day death).

Secondary Endpoint 1: Composite outcome of 28-day in-hospital mortality and postinjury multiple organ failure (MOF) incidence

- a. Definition: This outcome is defined as the occurrence of in-hospital death or MOF within the first 28 days postinjury. MOF is defined using the validated Denver MOF score (Denver MOF score>3 of simultaneously obtained scores after 48 hours postinjury).⁸⁰ Postinjury MOF remains the leading cause of late death among trauma patients, thus having a strong association with mortality.⁸⁵
- b. **Hypothesis 1:** The incidence of the composite outcome (28-day inhospital death or MOF) will be significantly higher[†] in control patients compared to experimental group patients.
- c. Statistical Analysis: Fisher Exact Test will be used to compare the incidence of this composite outcome in the two groups. Statistical significance will be determined according to the interim analyses procedures describe below. If adjustment for the pre-defined confounders (see Randomization Effectiveness in Section IV.D.2) is needed, we will use the above-defined method for categorical, binary variables.

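### Fisher's exact test is named for mortality and the composite under a rule written for Z: usable if mapped to the nominal alphas, but about 5 to 7 points less powerful than an exact unconditional Z test

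*Combined protocol and SAP*

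**What the plan says.** Section IV.E, item c (primary endpoint, statistical analysis): "The Fisher Exact test will be use to compare 28day mortality in the two groups". Section IV.F.1, item c, for the composite of in-hospital death or multiple organ failure: "Fisher Exact Test will be used to compare the incidence of this composite outcome in the two groups". Both items then defer: "Statistical significance will be determined according to the interim analyses procedures describe below".

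That procedure, in IV.D.5, works on a Z statistic: "At the final stage, the null hypothesis is rejected if Z falls into a rejection region". The design is "We planned 5 analyses (4 interim, 1 final), equally spaced, using the O'Brien-Fleming method to calculate two-sided boundaries", and a footnote makes all tests two-tailed.

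The November 2016 addendum in IV.E prints the current five-look table, headed "Spending = O'Brien-Fleming, N1 = 112, N2 =112, P1 = 0.12, P2 = 0.02, Continuity Correction". It lists Z boundaries of 4.877, 3.357, 2.680, 2.290 and 2.031, each beside a nominal alpha (0.042 at the final look), and total power of 0.800. It bases 112 per arm on 12% attrition, states a total of 224 (74 more than 150), and says three of the five analyses have taken place. Nowhere does the plan say how a Fisher p-value is to be set against a Z boundary.

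**The concern.** Two things are at stake.

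- **Specification.** A team could compute a pooled Z and compare it with 2.031, or compute a Fisher p-value and compare it with 0.042. The two can disagree on the same deaths, and the plan does not say which governs.
- **Power.** With event rates now near 12%, Fisher's test is strongly conservative. Section IV.I.1 already describes power for the primary endpoint as low, and the addendum adds 74 patients to restore it. Losing several points through the choice of test matters in that setting.

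**Working it through.** **Inputs.** Addendum in IV.E: 112 per arm, 12% against 2% mortality, 12% attrition, final boundary 2.031. Addendum in IV.F.1: composite 14% in controls, 11-point difference, so 14% against 3%. Evaluable per arm if attrition applies to the 112: 112 × 0.88 = 98.6, about 99.

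**1. The plan's own figure.** Integrating the five-look Z process over the printed boundaries returns a total alpha of 0.0500. Power of 80% needs a final-look drift of 2.836. With unpooled variance, 0.12×0.88 + 0.02×0.98 = 0.1252, and:

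- 99 evaluable, no correction: 0.10/√(0.1252/99) = 2.812, power 79.3%.
- 112 evaluable, 0.5/n correction: (0.10 − 0.00446)/√(0.1252/112) = 2.857, power 80.6%.
- 112 evaluable, full 1/n correction: (0.10 − 0.00893)/√(0.1252/112) = 2.724, power 76.7%.

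The stated 80% can therefore be reached by the first or second route, so the figure alone does not settle whether 112 means enrolled or evaluable.

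**2. Tests compared at the final look.** Nominal level 2×(1 − Φ(2.031)) = 0.0423. All 2×2 tables were enumerated.

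- Fisher: reject if the two-sided p ≤ 0.0423.
- Exact unconditional Z: Z = (p₁ − p₂)/√(2p̄(1 − p̄)/n). The p-value is the probability of |Z| at least as large as observed, maximised over the common event rate; reject if ≤ 0.0423. This is equivalent to a cut-off of |Z| about 2.05 at 112 or 99 per arm.

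| Endpoint | Evaluable per arm | Fisher | Exact Z | Gain (points) |
|---|---|---|---|---|
| Mortality 12% vs 2% | 112 | 80.2% | 86.1% | 5.9 |
| Mortality 12% vs 2% | 99 | 73.4% | 80.8% | 7.4 |
| Composite 14% vs 3% | 112 | 80.5% | 86.0% | 5.4 |
| Composite 14% vs 3% | 99 | 73.8% | 80.7% | 6.9 |

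Gains are taken before rounding.

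**3. Size at the final look.** Fisher: about 0.022 to 0.026 at null rates of 7 to 12%, maximum about 0.032 over all rates. Exact Z: maximum 0.0421 at 112 and 0.0414 at 99. Plain pooled Z judged at 2.031: maximum 0.044 at 112, slightly above the nominal level.

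**4. All five looks.** Mortality: Fisher 80.9% against exact Z 86.7% at 112, and 74.2% against 81.6% at 99. Composite: 81.2% against 86.6%, and 74.7% against 81.5%. The exact Z test's overall type I error stays at or below 0.0493. Fisher's is 0.024 to 0.031 at the planning rates, with a maximum of 0.034 to 0.037. The earlier looks do not remove the gap.

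**5. Disagreement on the same data.** At 112 per arm, 2 vs 9 deaths gives Z = 0.0625/√(2×0.0491×0.9509/112) = 2.16 but Fisher p = 0.059. Exact Z rejects and Fisher does not. The same split occurs at 3 vs 11 and 4 vs 12.

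**6. What can still be gained.** The addendum reports 88 of 100 patients analysable and mortality of 12% and 13% in groups A and B. Assume 44 evaluable per arm, 5 to 6 control and 6 to 7 plasma deaths so far, and 12% against 2% in everyone still to come. The chance of significance at the final test with 99 per arm is then about 1 to 5% with Fisher and 3 to 10% with exact Z, a gain of about 2 to 5 points. The arm split is not given in the documents, and group A is taken as control because the addendum's control rate of 12% matches it.

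**The case against.** A reader might infer that the final rule cannot be applied because Fisher's test yields no Z. The documents do not support that. Each boundary has a nominal alpha beside it, and the Fisher item refers to the interim procedure, so comparing p with nominal alpha is the natural reading. What remains is a missing sentence.

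A reader might also infer that the trial is certainly short of 80%. That depends on what 112 counts. The power run uses 112 and is labelled as continuity-corrected, and Fisher at 112 evaluable delivers 80.2%. On that reading the plan is coherent and the loss is unused power. Against it, the addendum presents 224 as a total over the existing 150. In the original table that 150 corresponds to 75 per arm with no attrition, falling to 68 and 60 evaluable as attrition rises. That favours reading 112 as enrolled, without proving it.

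The strongest objection is timing. Three of five analyses are reported as done, and mortality by group is printed. Changing the primary test now, to one that rejects more readily, is a change made after comparative data have been seen, and the computed error rates assume a test fixed in advance. This stands: the change is not free.

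Fisher is also an accepted, valid test that needs no large-sample argument at small early looks, and logistic regression replaces it if covariates are imbalanced. Both points limit the consequence but do not remove the gap.

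**Conclusion.** The point holds as a missing link between test and boundary together with an avoidable loss of planned power. Fisher is not an error, and type I error is not at risk under it.

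The loss is 5.4 to 7.4 points across both endpoints and both sample sizes, at the addendum's planning rates. At the final look Fisher uses about 52 to 62% of the nominal alpha at null rates of 7 to 12% (0.022/0.042 to 0.026/0.042). It uses about three quarters at its worst-case rate (0.032/0.042), so a claim that half the alpha is always wasted would go too far.

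If 112 per arm are enrolled and 12% are lost, the named test gives about 74% where 80% is stated, and exact Z keeps about 81%. If all 112 are evaluable, Fisher meets 80%.

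These are powers as seen from the start of the trial. They should not be read as what a change of test would now deliver; given the interim rates, the remaining gain is smaller.

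**What to change.** **Preferred.** For the remaining analyses, make the pooled (score) Z the test statistic for 28-day mortality and the composite. Judge it by its exact unconditional p-value against the nominal alpha of that look; at the final look the cut-off is |Z| about 2.05 at 112 or 99 evaluable per arm. Do not apply plain Z at 2.031, because its maximum size is 0.044. Make the change in a dated amendment, justified on operating characteristics alone and fixed before any further comparative data are seen. Report Fisher's result alongside at each remaining look.

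**Cost.** A short amendment, a short program and no extra patients. The real cost is to credibility: the primary test would change after three looks, with mortality by group already shown. The amendment should say so.

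**If Fisher is kept.** Add a sentence saying that its two-sided p-value is compared with the nominal alpha at each look. State whether 112 per arm means enrolled or evaluable. If enrolled, restate power as about 74% at 99 evaluable per arm for both endpoints.

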1) Group B experienced larger improvement in coagulopathy as measured by fibrinolysis from Field to ED (one of our secondary objectives, see below): as demonstrated by a repeated measures mixed linear model, the interaction between time and randomization approached significance, suggesting that group assignment modified the temporal trends of fibrinolysis as

measured by rTEG Ly30. Limiting the model to patients who presented in the Field in severe shock further increased the significance.

Linear Models for Repeated	ear Models for Repeated Measures including only Field and ED times for TEGs											
Model for LY30		ALL PATIE	ENTS		SEVERE SHOCK ONLY (Field SBP<=70mmHg)							
	Beta	SE	P-VALUE	Beta	SE	P-VALUE						
Intercept	6.7484	2.8959		6.2593	3.7915							
Time (ED, Field)	1.5018	2.9601	0.2528	4.9843	4.1149	0.5087						
Randomization (groups A, B)	3.3722	4.165	0.8321	7.0309	5.9547	0.9767						
Randomization*time (Interaction)	-8.1625	4.4787	0.0721	-14.3628	6.5971	0.0348						

2) Toleration of longer time to RBC **without** any adverse event, which was another of our secondary objectives (an objective of major importance to the military, and consequently to our funder, the Dept. of Defense)

There seemed to be a difference in time from injury and from ED arrival to the first required RBC favoring group B, who tolerated longer time without increasing mortality or any other adverse event. A survival analysis, however, did not reach significance.

More important, there has been no increase in adverse events or any suggestion of harm to enrollees and enrollment has been on target.

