- d. **Statistical test:** these outcomes are often skewed and non-normally distributed. Log transformation has been shown to be a good alternative to approximate normality for them. Thus, we will utilize linear regression to examine differences between the two groups. If adjustment for covariates is needed, we will proceed with the method for continuous normally distributed variables. In the case, normality cannot be achieved (as determined by the Shapiro-Wilk test for

^{†††} Although the hypothesis is worded as longer, the tests will be two-tailed to examine association in either direction.

normality), and there is no need to adjust for confounders, we will report median and interquartile ranges as measures of data central tendency and dispersion and use the Wilcoxon test to evaluate differences. If adjustment for covariates is needed, then we will resort to categorization of the outcomes, based on previously established, clinically meaningful cutoffs.⁸⁰ Overall experiment error will be adjusted for the number of adverse-outcomes-free-days parameters being analyzed using the Bonferroni method.

4. Temporal trends:

a. Coagulation Profile: We will assess temporal trends from pre-hospital coagulation variables (as described below) at 2, 4, 6, 12, 24, 72 hours and 28 days post-injury. The proposed coagulation measurements will also test the efficacy of plasma first resuscitation, since plasma is primarily employed for restoring levels of Factors II, V, VII, X and possibly XIII with a goal of greater than 20%, which is known to be effective for the cessation of surgical bleeding¹⁰⁷. In addition, there are major changes in the post-shock plasma affecting levels of proteins involved in regulating proteolysis, membrane lipid binding and stabilizing potentially cytotoxic intracellular components released after tissue injury.

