Our recent investigations of the proteome of three patients with significant hyperfibrinolysis, two who had ALI but survived and one who developed ARDS and did not, were compared to healthy controls of the same gender. The hyperfibrinolytic state of these injured patients was confirmed by thrombelastograms (TEG) prior to blood component resuscitation (results not shown). The proteins that significantly increase in the patient plasma vs. normal males include: actin (15-28-fold), a cytoplasmic protein that has been implicated in ALI when free in the circulation, von Willebrand Factor (15-24-fold), a necessary coagulation factor, α -enolase (10-28-fold)⁵⁹ a lyase with protease activity, perioxiredoxins 2 & 6 (7-14-fold), proteins which are atypical phospholipases, adiponectin (8-19-fold), which is a hormone from adipocytes that is important in glucose uptake & insulin sensitivity, PPAR1/PPAR2 lipid oxidation and is а ligand. matrix metalloproteinase-9 (MMP-9) (3-5-fold) that is also known as gelatinase, which breaks down the extracellular matrix and is a sensitive indicator of leukocyte activation and, lastly, carboxypeptidase β2, also known as TAFI. Plasma contains many proteins which can oppose the actions of these proteins, including: anti-proteases (a1antitrypsin, a2-macroglobulin, and other globulins), lipid carriers (albumin), and gelsolin which solubilizes and inhibits actin induced ALI.^{57, 58, 60, 108}

1. **Hypothesis**: Experimental group patients will demonstrate earlier and larger improvement in coagulation variables compared to control patients.

2. Statistical analysis: variables will be examined for normality through the Shapiro-Wilk test and log-transformed if necessary to approximate normality. Statistical analyses will be performed by using mixed linear models (SAS Proc Mixed), with an unstructured covariance structure between the different time measures, and if needed, adjustment for potential confounders in case randomization fails to account for differences. Overall experiment error will be adjusted for the number of coagulation parameters being analyzed using the Bonferroni method. Multiple comparison adjustment within each coagulation variable temporal trend will be done using the Tukey's method.

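### The LY30 trend is a change from unequal Field values: adjusting for the Field value makes it about 27–35% smaller, and the planned trend model does not say how the Field value is handled

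*Combined protocol and SAP*

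**What the plan says.** The addendum of 16 November 2016, in IV.E under Sample Size and Power, lists two promising trends before it proposes to enlarge the trial. The first is that "Group B experienced larger improvement in coagulopathy as measured by fibrinolysis from Field to ED". It rests on a repeated-measures model with only the Field and ED values of LY30. The rows print beta, SE and p for all patients, then for patients with field SBP of 70 mmHg or less:

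- The row for the sampling occasion reads "Time (ED, Field) 1.5018 2.9601 0.2528 4.9843 4.1149 0.5087".
- The row for the study arm reads "Randomization (groups A, B) 3.3722 4.165 0.8321 7.0309 5.9547 0.9767".
- The row for the arm-by-occasion term reads "Randomization*time (Interaction) -8.1625 4.4787 0.0721 -14.3628 6.5971 0.0348".

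The text given here shows no reference levels and no means by arm.

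For the final analysis, IV.G.4.a states "We will assess temporal trends from pre-hospital coagulation variables". IV.G.4.a.2 adds "Statistical analyses will be performed by using mixed linear models (SAS Proc Mixed), with an unstructured covariance structure between the different time measures", with adjustment for confounders if needed. It does not give the fixed effects or say how the Field value enters. The covariates in IV.D.2 and IV.D.6 include "degree of shock (Field SBP, Field Heart rate, Field Hematocrit), and a field coagulation measure (Field INR") but not Field LY30. A listed covariate is used only if the arms differ at p<0.05 or the DSMB judges the difference clinically significant.

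**The concern.** In this model the interaction equals the arm gap at ED minus the arm gap in the field. Randomisation gives both arms the same expected Field value, so a Field gap is chance. When the Field means are left free, that gap is carried into the effect at full weight. If the Field–ED correlation is well below 1, part of the gap would be expected to close without any plasma effect.

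The interaction is offered in support of continuing the trial, and the severe-shock p of 0.0348 is the only one in the table below 0.05. The groups are labelled A and B, but the addenda take group A's values (12% mortality, INR 1.32, 18% with INR above 1.5) as those of the control group, so readers will take the sentence as a plasma effect. Coagulopathy is study aim 1, and IV.I.1.c lets significant exploratory results count towards calling the therapy promising. It therefore matters how the final trend models treat the Field value.

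**Working it through.** **Inputs.** All are from the LY30 table; the intercepts are 6.7484 and 6.2593. Improvement is read as a fall in LY30.

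**1. Reproduce the interaction p-values.** All patients: t = −8.1625/4.4787 = −1.82; the printed 0.0721 corresponds to about 80 df. Severe shock: t = −14.3628/6.5971 = −2.18; the printed 0.0348 corresponds to about 45 df. The df are not printed; these are solved values.

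**2. Establish the coding.** The main-effect p-values are not those of beta/SE (Time would give 0.61 and 0.23; Randomization 0.42 and 0.24). They are Type 3 tests, averaged over the other factor. For Time, the estimate is beta + interaction/2, with SE = interaction SE/2:

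- All: 1.5018 − 4.0813 = −2.579, SE 2.239, p = 0.2528 (printed 0.2528).
- Severe: 4.9843 − 7.1814 = −2.197, SE 3.299, p = 0.5088 (printed 0.5087).

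So the model uses 0/1 reference coding, and the Randomization beta is the arm gap at one time point.

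**3. Cell means.** Two choices of reference cell make the quoted sentence true.

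| | Reference Field, A | Reference ED, B |
|---|---|---|
| All: A, Field to ED | 6.75 to 8.25 | 3.46 to 10.12 |
| All: B, Field to ED | 10.12 to 3.46 | 8.25 to 6.75 |
| All: gap B−A, Field; ED | +3.37; −4.79 | +4.79; −3.37 |
| Severe: A, Field to ED | 6.26 to 11.24 | 3.91 to 13.29 |
| Severe: B, Field to ED | 13.29 to 3.91 | 11.24 to 6.26 |
| Severe: gap B−A, Field; ED | +7.03; −7.33 | +7.33; −7.03 |

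The Field gap as a share of the interaction is 3.37/8.16 = 41% or 4.79/8.16 = 59% (all), and 7.03/14.36 = 49% or 7.33/14.36 = 51% (severe).

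**4. Recover the second variance and the covariance.** Let V1 and V2 be the variances of the gaps at the reference time and the other time, and C their covariance. Then V1 + V2 − 2C = (interaction SE)², and V1 + V2 + 2C = 4 × (SE of the average gap)². The SE of the average gap follows from the printed Type 3 Randomization p.

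- All: average gap 3.3722 − 4.0813 = −0.709; p = 0.8321 gives SE 3.334. Hence V1 = 4.165² = 17.35, V2 = 14.91 (SE 3.861), C = 6.10, correlation 0.38.
- Severe: average gap 7.0309 − 7.1814 = −0.1505; p = 0.9767 gives SE 5.124. Hence V1 = 5.9547² = 35.46, V2 = 38.82 (SE 6.230), C = 15.38, correlation 0.41.

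Gaps at one time point: in all patients, 3.37 has p = 0.42 and 4.79 has p = 0.22; in severe shock, 7.03 has p = 0.24 and 7.33 has p = 0.25. Depending on the coding, each is the Field gap or the ED gap. None is significant, and none would meet the p<0.05 adjustment trigger even if Field LY30 were listed.

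**5. Adjust for the Field value.** With V_F and V_E the Field and ED gap variances: b = C/V_F; estimate = ED gap − b × Field gap; variance = V_E − C²/V_F.

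| | b | Estimate (SE) | p | Reduction from printed |
|---|---|---|---|---|
| All, reference Field, A | 0.352 | −4.79 − 0.352 × 3.37 = −5.98 (3.57) | 0.10 | 27% |
| All, reference ED, B | 0.409 | −3.37 − 0.409 × 4.79 = −5.33 (3.85) | 0.17 | 35% |
| Severe, reference Field, A | 0.434 | −7.33 − 0.434 × 7.03 = −10.38 (5.67) | 0.07 | 28% |
| Severe, reference ED, B | 0.396 | −7.03 − 0.396 × 7.33 = −9.94 (5.42) | 0.07 | 31% |

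**6. Precision.** Variance of the interaction over variance of the adjusted estimate: 4.4787²/3.57² = 1.57 and 4.4787²/3.85² = 1.35 (all); 6.5971²/5.67² = 1.35 and 6.5971²/5.42² = 1.48 (severe).

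**The case against.** The case against has real force.

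- Difference in change is unbiased over repeated randomisation, so the model is not invalid. This stands. The criticism is of precision and of what the estimate means given the imbalance that occurred.
- The printed p-values of 0.8321 and 0.9767 beside the Randomization betas might suggest that the table conceals the Field gap. It does not: they are ordinary Type 3 tests, as step 2 shows for Time.
- A reader might take the 41–59% share as the size of the distortion. It is only a decomposition. Adjustment removes about a third or less, and the rest stays in the same direction.
- A reader might infer that the final trend analysis will leave the Field means free. IV.G.4.a.2 gives no fixed effects, and the same procedure can be fitted with a common Field mean. The plan is silent; it is not committed to the weaker model.
- Means by arm may exist in the figure missing just before this item or in the interim report that the addendum cites. Their absence here is no fault in the plan.
- The consequences are limited. The addendum says only that the interaction approached significance, no sample-size calculation uses LY30, and the temporal trends are exploratory with multiplicity adjustment. This stands too, and it makes the point an improvement to the analysis, not a threat to the trial.

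**Conclusion.** The concern holds as a free improvement. The LY30 interaction includes a Field gap that favours the reported conclusion, and the arms do not differ significantly at ED alone (p about 0.22–0.42; severe shock about 0.24–0.25). After adjustment for the Field value the effect is about 27–35% smaller in all patients and 28–31% smaller in severe shock. Its p-value is about 0.10–0.17 instead of 0.072, and about 0.07 instead of 0.035, so the nominal significance in severe shock is lost. A trend in the same direction remains; the figures do not show it to be spurious.

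The adjusted figures are back-solved from rounded betas, SEs and Type 3 p-values. They assume complete Field–ED pairs and the solved df. They also take the Field sample as drawn before any study fluid, which IV.B.1.d implies but does not state outright. The direction is conditional on the addendum's sentence: with the other reference cells (Field, B or ED, A), the same betas would give group A the larger fall.

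For the final analysis, the supported statement is that the plan has no written rule for each variable's own Field value and so does not prevent the same analysis.

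**What to change.** In IV.G.4.a.2, state that the mixed model is fitted with the Field mean constrained equal in both arms, keeping arm-by-time terms only after baseline. Alternatively, enter each variable's own Field value as a covariate regardless of any imbalance test. Report the arm difference at ED and at later times with its confidence interval.

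Re-run the addendum's LY30 table in the same way for all patients and for severe shock. State the reference levels, give the four cell means, and label the main-effect p-values as Type 3 tests. Reword the larger-improvement sentence to match the adjusted estimate.

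The cost is one model statement, one re-run table and a few lines of text. It needs no new data and changes no boundary, sample size, or primary or secondary test. On the figures above, the LY30 p-values would become somewhat less favourable, while later trend estimates should gain precision.
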